Planned study period First subject first visit (FSFV) Q2 2018 Last subject last visit (LSLV) Q3 2022	Clinical Phase Observational study
Background and Scientific Justification for Conducting the Study The rationale for the current protocol is to collect data from extended follow up in subjects that have received a kidney transplant following imlifidase dosing to provide a better understanding regarding the long-term outcome for these subjects. Data of parameters such as patient and graft survival, comorbidity, treatment of graft rejection episodes and quality of life as well as anti-drug antibody levels will be collected. This prospective, observational follow up study of subjects who have received imlifidase prior to kidney transplantation will provide important data to future prescribers and patients of the potential long-term benefits of imlifidase mediated transplantation.	
Primary objective: Evaluation of graft survival in subjects who have undergone kidney transplantation after imlifidase administration.	
Secondary Objectives: 
• Evaluation of long-term clinical outcomes of transplanted subjects treated with imlifidase in terms of patient survival, kidney function, comorbidity, treatments and quality of life.• Assessment of safety blood sampling in transplanted subjects treated with imlifidase• Assessment of donor specific antibodies (DSA) in transplanted subjects treated with imlifidase• Assessment of immunogenicity (anti-drug antibodies, ADA) in transplanted subjects treated with imlifidase	
Endpoints The primary endpoint of this study is to determine overall graft survival, defined as time from transplantation to graft loss at 1, 2, 3 and 5 years after first dose of imlifidase. Graft loss is defined as: Permanent return to dialysis for at least 6 weeks, re-transplantation, or nephrectomy.	

Secondary Endpoints

The following secondary endpoints will be evaluated at 1, 2, 3 and 5 years from the first dose of imlifidase:

- Overall patient survival (time from transplantation to death for any cause)
- Kidney function as evaluated by eGFR, P-creatinine, proteinuria
- Number of graft rejection episodes (Banff classification)
- Safety laboratory tests
- Treatment of graft rejection episode
- Comorbidity
- DSA levels
- Presence of BK virus
- ADA as evaluated by anti-imlifidase IgG
- Health related quality of life as evaluated by patient questionnaires

Methodology

This is a five year, long-term follow up, observational study. The study will primarily determine the time of graft survival in subjects who have received imlifidase prior to kidney transplantation.

Subjects that have participated, or are currently participating, in the imlifidase kidney transplantation studies (called feeder studies) 13-HMedIdeS-02, 13-HMedIdeS-03, 14-HMedIdeS-04 and 15-HMedIdeS-06 will be included. The subjects will attend 4 follow up visits, 1, 2, 3 and 5 years after imlifidase administration.

Study Procedures/Assessments

At all visits, graft function (creatinine, eGFR, proteinuria) and time of graft survival will be assessed. Blood samples for analysis of DSAs, ADA and antibodies towards BK virus will be taken as well as total IgG and hematology samples. Information about patient survival, comorbidity (infections, malignancy, diabetes mellitus and cardiovascular events) and treatments of graft rejection episode (dialysis, plasmapheresis, medications) will be recorded. The subjects will be asked to complete QoL questionnaires.

Number of subjects

Up to 46 subjects will be included depending on subjects' willingness to participate in the study.

Diagnosis and main criteria for inclusion/exclusion

Inclusion Criteria:

- 1) Signed Informed Consent obtained before any study-related procedures
- 2) Previous dosing with imlifidase followed by kidney transplantation and participation in one of the following clinical studies: 13-HMedIdeS-02, 13-HMedIdeS-03, 14-HMedIdeS-04 or 15-HMedIdeS-06

Exclusion Criteria:

- 1) Individuals deemed unable to comply with the protocol
- 2) Inability by the judgment of the investigator to participate in the study for other reasons

Medicinal Product(S)

Not applicable

Statistical methods

This is a long-term non-interventional study and for the evaluation and presentation of data descriptive techniques will be used. The data from the clinical assessments will be summarised by feeder study and time point. Summary statistics (n, arithmetic mean, standard deviation, median, minimum and maximum values) will be presented for continuous variables. Counts and, if relevant, percentages will be presented for categorical variables. The primary endpoint will be analysed by the Kaplan-Meier survival method. There will be no formal statistical hypothesis or testing because of the observational nature of the study.

Table of contents

See Appendix 1 “Protocol Amendment History” for details of Amendment 03.	2

IdeS	Immunoglobulin G degrading enzyme of Streptococcus pyogenes
IEC	Independent Ethics Committee
IMP	Investigational Medicinal Product
IRB	Institutional Review Board
IVIg	Intravenous Immunoglobulin
KDQOL-SF	Kidney Disease Quality of Life-Short Form
KM	Kaplan-Meier
LD	Living Donor
MedDRA	Medical Dictionary for Regulatory Activities
MFI	Mean Florescence Intensity
PE	Plasma Exchange
QA	Quality Assurance
RA	Regulatory Authority
SAB	Single Antigen Bead
SAE	Serious Adverse Event
SAP	Statistical Analysis Plan
SDV	Source Document Verification
SUSAR	Suspected Unexpected Serious Adverse Reaction

1. INTRODUCTION

The company code initially used in this project was HMED-IdeS (sometimes abbreviated to IdeS) and thus many reports refer to this name. The International Nonproprietary Name (INN) imlifidase was recently assigned for the active substance and going forward this name will be used.

1.1 Background

Renal transplantation is the preferred treatment choice for patients with end stage kidney disease since it increases survival and patient quality of life and results in substantial savings in health care costs compared to dialysis ([Montgomery et al. 2005](#)).

Approximately one third of patients waiting for kidney transplantation are sensitized to human leukocyte antigen (HLA) and sensitization hampers the identification of a suitable donor ([Iyer et al. 2014](#)). The presence of strong HLA donor specific antibodies (DSAs) is a direct contraindication to transplantation because of the risk of hyper-acute antibody-mediated rejection with acute allograft loss. For transplant candidates who have antibodies, which react against a wide range of HLA, it can be difficult to find a donor against whom they have no antibodies. This is true both for patients waiting for a deceased donor kidney and for those within a paired donation program who have an available live donor against which they have DSAs.

Data demonstrates that desensitization followed by transplantation of patients with DSAs is clearly associated with short- and long-term survival benefits compared to staying on dialysis ([Montgomery et al. 2011](#); [Vo et al. 2013](#); [Orandi et al. 2014](#); [Orandi et al. 2016](#)). In addition, the patient's quality of life is dramatically increased and there are substantial cost-savings associated with desensitization compared to dialysis ([Vo et al. 2013](#)).

Imlifidase is an IgG-degrading enzyme of *Streptococcus pyogenes* that cleaves all four human subclasses of IgG with strict specificity. Cleavage of IgG generates one F(ab')₂- and one homodimeric Fc-fragment and efficiently neutralizes Fc-mediated activities of IgG (HMed doc. No. 2012-003) ([Wenig et al. 2004](#); [Vincents et al. 2004](#); [von Pawel-Rammingen et al. 2002](#)). Imlifidase-mediated IgG degradation constitutes a novel therapeutic principle for the treatment of IgG-driven human diseases.

Hansa Biopharma AB has performed *in vitro* studies and clearly demonstrated that imlifidase effectively cleaves purified IgG as well as IgG in serum from human and rabbit. Imlifidase is very specific in that no other substrate has been found (HMed Doc. No. 2012-003). In addition, imlifidase treatment rapidly and substantially cleaved anti-HLA IgG in serum from sensitized chronic kidney disease (CKD) grade 5 patients *in vitro* (HMed Doc. No. 2012-005).

The reactivity to individual HLA-antigens was reduced below the critical Mean Florescence Intensity (MFI) acceptable for transplantation and a positive crossmatch test was turned into negative. Imlifidase offers a unique and powerful approach for removing the impenetrable immunology barrier HLA antibodies present and would allow potentially life-saving transplants to highly sensitized patients who are currently not eligible for kidney transplantation.

The clinical studies performed or ongoing with imlifidase within the transplantation program are summarised in [Table 1](#).

Table 1. Summary table of clinical studies with imlifidase in the transplantation program.

Study No / EudraCT No	Phase / Subjects	Doses / Follow up time	Main objectives	Comments	Status / Country / Subject Numbers
11-HMedIdeS-01 / 2012-000 969-21	I / Healthy subjects	0.010, 0.040, 0.12 and 0.24 mg/kg BW 64 d	Safety	First-in-man, double blind, randomized, single ascending dose, 20 active, 9 placebo. IgG completely cleaved within 1-2 h. Safe and well tolerated.	Completed / SE / N=29
13-HMedIdeS-02 / 2013-005417-13	II / CKD Patients	0.12 and 0.25 mg/kg BW given once or twice within 48 h / 64 d	Efficacy in CKD patients defined as imlifidase dosing scheme resulting in HLA antibody levels acceptable for transplantation, within 24 h from dosing. Safety in the transplantation setting.	Single arm with ascending doses. Primary efficacy endpoint reached. Safe and well tolerated. One patient was transplanted (not part of protocol). Deceased donor.	Completed / SE / N= 8
13-HMedIdeS-03 / 2014-000712-34	II / Patients	0.25 and 0.5 mg/kg / 180 d	Safety in the transplantation setting. Efficacy defined as HLA antibody levels acceptable for transplantation.	Similar design as 13-HMedIdeS-02 but transplantation part of protocol. Deceased and living donors. Safe and well tolerated. All patients desensitized and transplanted	Completed / SE / N=10

Study No / EudraCT No	Phase / Subjects	Doses / Follow up time	Main objectives	Comments	Status / Country / Subject Numbers
14-HMedIdeS-04 / EudraCT: NA IND 124301	II / Patients	0.24 and 0.5 mg/kg / 180 d	Safety in combination with Cedars Sinai's “standard protocol” for desensitization of highly sensitized patients. Efficacy in prevention of ABMR.	Investigator sponsored IND. Imlifidase combined with rituximab and IVIg. All transplantations successful except one graft loss which occurred due to non- HLA and non-IgG ABMR. Biopsy suggested rejection due to IgM and IgA.	Completed / US / Total N=17 Analysis and reporting ongoing.
15-HMedIdeS-06 / 2016-002064-13 IND: 128074	II / Patients	0.25 and 0.5 mg/kg / Primary endpoint: 24 h Safety: 180 d	Efficacy in creating a negative crossmatch test. Safety in the transplantation setting.	Deceased and living donors. Target population cannot be transplanted with current available methods for desensitization. All transplantations (18) were successful except one graft loss. For one patient, imlifidase dosing was interrupted due to allergic reaction and the patient was not transplanted.	Ongoing / US, FR & SE / Total N=19 Recruitment ended 15 Dec 2017.

BW=body weight, h=hours, d=days

In completed (13-HMedIdeS-02, 13-HMedIdeS-03 and 14-HMedIdeS-04) and ongoing studies (15-HMedIdeS-06), subjects have been treated with imlifidase and transplanted with kidneys from deceased or living donors. The follow up periods were 6 months post transplantation except for 13-HMedIdeS-02 with 2 months follow up. The current protocol aims at collecting key information regarding overall graft function and safety from all subjects that have been treated with imlifidase prior to kidney transplantation.

1.2 Rationale

The rationale for the current protocol is to collect data from extended follow up in subjects that have received a kidney transplant following imlifidase dosing to provide a better understanding regarding the long-term outcome for these subjects. Data of parameters such as patient and graft survival, kidney function, comorbidity, treatment of graft rejection episodes and quality of life as well as anti-drug antibody levels will be collected.

1.3 Benefit / Risk Aspects

The subjects included in this study have received imlifidase prior to kidney transplantation in previous clinical studies. The current study is performed to collect long-term follow up data on graft function and safety. Most of the assessments performed under the current protocol are already part of the follow up within standard of care for these subjects and consequently they will not impose any additional risk.

2. STUDY OBJECTIVES AND ENDPOINTS

2.1 Objectives

Primary Objective

The primary objective of this study is to evaluate graft survival in subjects who have undergone kidney transplantation after imlifidase administration.

Secondary Objectives

The secondary objectives include:

- Evaluation of long-term clinical outcomes of transplanted subjects treated with imlifidase in terms of patient survival, kidney function, comorbidity, treatments and quality of life.
- Assessment of safety blood sampling in transplanted subjects treated with imlifidase
- Assessment of donor specific antibodies (DSA) in transplanted subjects treated with imlifidase
- Assessment of immunogenicity (anti-drug antibodies, ADA) in transplanted subjects treated with imlifidase

2.2 Endpoints

Primary Endpoint

The primary endpoint of this study is to determine overall graft survival, defined as time from transplantation to graft loss at 1, 2, 3 and 5 years after first dose of imlifidase.

Graft loss is defined as: Permanent return to dialysis for at least 6 weeks, re-transplantation, or nephrectomy. If dialysis is used to define graft loss, the date of graft loss will be the first day of the last ongoing dialysis period reported ([EMA Guideline on clinical investigation of immunosuppressants for solid organ transplantation 2008](#)).

Secondary Endpoints

The following secondary endpoints will be evaluated after the first dose of imlifidase at the time points 1, 2, 3 and 5 years:

- Overall patient survival defined as time from transplantation to death for any cause

- Kidney function as evaluated by eGFR, P-creatinine, proteinuria
- Number of graft rejection episodes (classified by Banff, [\(Haas et al. 2018\)](#))
- Safety laboratory tests (hematology, total IgG)
- Treatment of graft rejection episodes
- Comorbidity
- DSA levels as evaluated by SAB-HLA analysis
- Presence of BK virus
- ADA as evaluated by anti-imlifidase IgG
- Health related quality of life (HR-QoL) as evaluated by patient questionnaires EQ-5D-5L and KDQOL-SF.

3. INVESTIGATIONAL PLAN

3.1 Overall Study Design

This is a five year, long-term follow up, observational study. Centers that have participated, or are currently participating, in selected imlifidase kidney transplantation studies (referred to as “feeder studies”) will be contacted and requested to approach subjects for enrolment in the study. The following studies will be considered feeder studies: 13-HMedIdeS-02, 13-HMedIdeS-03, 14-HMedIdeS-04 and 15-HMedIdeS-06. Up to 46 subjects will be included depending on subjects’ willingness to participate in the study.

The study will primarily determine the time of graft survival in subjects who have received imlifidase prior to kidney transplantation. The subjects will attend 4 follow up visits, 1, 2, 3 and 5 years after imlifidase administration. Some subjects will not perform all 4 visits because the study start will be after the subjects’ first visit should have taken place.

Kidney function (creatinine, eGFR, proteinuria) and graft survival will be assessed. Graft rejection episodes will be determined by Banff classification. Information from kidney biopsies performed within standard of care will be collected. Blood samples for analysis of DSAs, ADA and antibodies towards BK virus will be taken as well as total IgG and safety hematology samples. Medically relevant comorbidity (infections, malignancy, diabetes mellitus and cardiovascular events) will be recorded. Information about treatments of graft rejection episodes will be recorded (dialysis, plasmapheresis, medications). At all visits, the subjects will be asked to complete QoL questionnaires. The overall study outline is summarized in Figure 1.

3.1.1 Overall Study Outline

[figure not shown]

Figure 1.Overall study outline

3.1.2 Follow up Procedures

The study subjects will be followed up according to clinical standard of care during and after study completion.

3.2 Study Schedule

Planned first subject first visit:	Q2 2018
Planned recruitment period:	NA
Planned last subject last visit:	Q4 2022
Planned completion of the Clinical Study Report:	Q4 2023

3.3 Planned number of study sites and subjects

There will be 6 study sites involved in the study; 2 in Sweden, 1 in France and 3 in US. In total, up to 46 male and female subjects will be asked to participate.

3.4 Planned End of Study

The planned End of Study is defined as last subject last visit. Hansa Biopharma will ensure that End of Study notification is submitted to the concerned regulatory authorities and IEC/IRB according to local requirements.

For procedures in case of premature termination or suspension of the study, see [Section 12.4](#).

4. STUDY POPULATION

4.1 General

Subjects who have received imlifidase prior to kidney transplantation in a feeder study will be included. The subjects will be approached, and informed consent will be obtained for participation in the current study. Up to 46 subjects will be included depending on subject willingness to participate.

4.2 Selection Criteria

Subjects must meet all inclusion criteria and no exclusion criteria to be eligible for the study.

4.2.1 Inclusion Criteria

- Signed Informed Consent obtained before any study-related procedures
- Previous dosing with imlifidase followed by kidney transplantation and participation in one of the following clinical studies: 13-HMedIdeS-02, 13-HMedIdeS-03, 14-HMedIdeS-04 or 15-HMedIdeS-06

Note: The primary objective in this study is overall graft survival after imlifidase treatment therefore the subjects can also be included in the event that the subject did not fully complete the feeder study.

4.2.2 Exclusion Criteria

- Individuals deemed unable to comply with the protocol
- Inability by the judgement of the investigator to participate in the study for other reasons

4.3 Discontinuation of Subjects

The subjects have the right to withdraw from the study at any time for any reason, without the need to justify their decision. However, the investigator should record the reason for the subject's withdrawal, if possible. The investigator also has the right to withdraw subjects. In either event, the investigator must notify monitor.

If a subject prematurely discontinues participation, the End of Study Form (with date and reason for discontinuation) in the CRF must be completed.

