5. STUDY PROCEDURES

5.1 Study Visits

For each subject the duration of the study will not exceed 5 years and 6 months post imlifidase dosing.

All subjects considered for the study must be informed about the study, verbally and in writing, and give their written consent before any study procedure is performed. After informed consent is obtained, pre-study visit data such as information on graft survival and patient survival can be collected and entered in the CRF.

Some subjects will not perform all 4 visits because the study start will be after the subjects' first visit should have taken place.

If a subject is not able to attend a planned visit at the site, the visit can be performed remotely. The blood sampling should be performed at the local laboratory (if possible) and QOL forms

sent to the subject. The following activities and assessments will be performed at **1 year** (+/- 2 months), **2 years** (+/- 4 months), **3 years** (+/- 4 months) and **5 years** (+/- 6 months) **post imlifidase dosing:**

- Check of inclusion and exclusion criteria will be performed at the first visit for each subject after 1, 2 or 3 years post imlifidase dosing.
- Subjects shall complete QoL questionnaires (EQ-5D-5Land KDQOL-SF)
- Evaluation of graft survival
- Record patient survival (if applicable, date and cause of death)
- Safety laboratory tests (see Table 3)
- P-creatinine, eGFR and U-proteinuria tests
- DSA samples
- ADA sample
- BK virus sample
- Record comorbidity such as infections, malignancy, diabetes mellitus and cardiovascular events
- Record graft rejection episodes (classified by Banff)
- If applicable, record information from standard of care kidney biopsy reports
- Record treatments of graft rejection episodes (PE, IVIg, dialysis, other)
- Record current immunosuppressive medication
- Record and report AEs caused by study procedure or a clinically significant safety lab value

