5.2 Flow Chart

Table 2. Study flow chart.

Visit post imlifidase dosing	1 year ¹	2 years	3 years	5 years
Visit window	(+/- 2 months)	(+/- 4 months)	(+/- 4 months)	(+/- 6 months)
Informed consent	x ²			
Eligibility	x ²			
Enrollment and allocation of patient number	x ²			
QoL questionnaires (EQ-5D-5L, KDQOL-SF)	x	x	x	x
Patient survival status	x ³	x	x	x
Graft survival status	x ³	x	x	x
Graft rejection episodes ⁴	x	x	x	x
Kidney biopsy reports ⁵	x	x	x	x
P-creatinine, eGFR calculation (performed by Sponsor)	x	x	x	x
Proteinuria (dipstick)	x	x	x	x
Hematology (Hemoglobin, Diff of leukocytes, Thrombocytes)	x	x	x	x
Total IgG	x	x	x	x
BK test	x	x	x	x
DSA (HLA antibody, Luminex) central lab	x	x	x	x
DSA (HLA antibody, Luminex) local lab	x	x	x	x
ADA (Anti-imlifidase IgG) central lab	x	x	x	x
Comorbidity ⁶	x	x	x	x
Current immunosuppressive medication	x	x	x	x
Treatment of graft rejection episode (PE, IVIg, dialysis, other)	x	x	x	x
Adverse events ⁷	x	x	x	x

¹. Some subjects will not perform all 4 visits because the study start will be after the subject's first visit should have taken place. If applicable, record creatinine and proteinuria results from planned time for 1- and 2 Years visits. End of Study (EOS) will occur 5 years (+/- 6M) after transplantation or earlier in the case of death, withdrawal of consent or lost to follow up.

². These activities shall be performed at subject's first visit that can take place 1, 2, or 3 years post imlifidase dose depending on when the subject was transplanted in the feeder study.

³. After informed consent is obtained, pre-study visit data such as information on graft survival and patient survival can be collected and entered in the CRF. If applicable, record cause and date of death.

⁴. Record biopsy proven graft rejection episodes (classified by the Banff classification) and creatinine and proteinuria results from the episode.

⁵. If standard of care kidney biopsies are performed for any reason, at any time-point, e.g. suspected rejections, record information in the CRF.

⁶. Record comorbidities that are medically relevant and registered in the subject's medical record. Medically relevant comorbidity are infections, malignancy, diabetes mellitus and cardiovascular events.

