### 4.2 Subject disposition

The number of subjects in FAS will be summarized by feeder study. All 46 subjects from feeder studies that are eligible for the extension study will be accounted for. Furthermore, the number of subjects who withdraw from this study will be summarised overall, by withdrawal time, by reason for withdrawal and by feeder study.

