### 4.4 Endpoints

#### 4.4.1 Primary endpoint

The primary endpoint, overall graft survival, is defined as time from transplantation to graft loss evaluated at 1, 2, 3 and 5 years after first dose of imlifidase. Graft loss is defined as: Permanent return to dialysis for at least 6 weeks, re-transplantation or nephrectomy. If dialysis is used to

define graft loss, the date of graft loss will be the first day of the last ongoing dialysis period reported. The graft loss is evaluated at 1, 2, 3, and 5 years after dosing, but the time will be recorded as duration in days.

The primary endpoint will be analysed by the Kaplan-Meier survival method for the combined group with all feeder studies. The overall graft survival will be tabulated and presented graphically as a KM plot with 95% confidence limits, indicating the risk set per year and marking the censored observations. The following events will be censored at the time of occurrence: withdrawal from the study without graft loss, death not caused by graft loss, evaluation time point (the yearly evaluations - only for the annual reports not in the final reporting of the study) and end of study without graft loss. The survival percentage with 95% CI will be estimated at 1, 2, 3 and 5 years, or, for the yearly summary analyses as far as data allows.

The reason for graft loss will be displayed in a listing.

The protocol stipulates that explorative modelling of the influence of covariates on the graft loss may be defined in the SAP. With a maximum sample size of 46 patients and an expected small proportion of patients with graft loss, estimation of covariate parameters may be highly variable in which case the explorative modelling will not be performed.

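### Investigator withdrawal is allowed without criteria, is not among the listed reasons for early End of Study, and has no provision for later graft and vital status, leaving the survival curves open to avoidable, possibly informative censoring

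*Protocol*

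**What the plan says.** **When a subject leaves.** After giving subjects the right to withdraw, Protocol 4.3 adds: "The investigator also has the right to withdraw subjects". No criteria follow. The monitor is to be notified, and then: "If a subject prematurely discontinues participation, the End of Study Form (with date and reason for discontinuation) in the CRF must be completed". The section does not say whether graft or vital status is still collected.

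**When the study ends for a subject.** Footnote 1 of the flow chart (Protocol 5.2, repeated in SAP 2.1) puts End of Study at 5 years after transplantation, with a 6-month window, "or earlier in the case of death, withdrawal of consent or lost to follow up".

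**How withdrawal is analysed.** Protocol 11.5 and SAP 4.4.1 censor at the time of occurrence, among other events, "withdrawal from the study without graft loss, death not caused by graft loss". SAP 4.4.2 handles graft loss not censored for death in the same way, and censors patient survival at withdrawal while alive. On the main result SAP 4.4.1 says: "The survival percentage with 95% CI will be estimated at 1, 2, 3 and 5 years".

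**Related provisions.** SAP 4.2 states that "the number of subjects who withdraw from this study will be summarised overall, by withdrawal time, by reason for withdrawal and by feeder study". Protocol 5.1 allows remote contact: "If a subject is not able to attend a planned visit at the site, the visit can be performed remotely". Protocol 3.1.2 adds: "The study subjects will be followed up according to clinical standard of care during and after study completion".

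**The concern.** Section 4.3 and footnote 1 do not match. An investigator-withdrawn subject gets an End of Study Form under 4.3 for a reason that the footnote does not give.

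The larger issue is what happens to the endpoint. Kaplan-Meier censoring assumes that censored subjects carry the same later risk as those still followed. A discretionary withdrawal could be related to adherence or to the course of the graft, and then the assumption fails. Because the rule censors at the withdrawal itself, a later graft loss would stay outside the primary curve even if the site knew of it. The same applies to later deaths in the other two curves.

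The documents give no reason for an investigator's decision to cost the study its primary outcome. No imlifidase is given here, standard-of-care follow-up continues, and visits can be remote. The plan accepts outcome data outside visits elsewhere: the note to Protocol 4.2.1 admits subjects who did not complete a feeder study because graft survival is the objective, and 5.1 allows pre-visit graft and patient survival to be entered after consent.

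**Working it through.** **1. The plan's own figure.** There is no powered sample size. The maximum of 46 is the count of transplanted feeder-study subjects in Protocol Table 1: 1 (study 02) + 10 (study 03) + 17 (study 04) + 18 (study 06) = 46. It reproduces.

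**2. What is provided after discontinuation.**
- Pregnancy outcome: followed even after discontinuation (Protocol 8.4).
- Adverse events leading to discontinuation: followed until they resolve, stabilise or return to baseline (8.2.4).
- Graft and vital status: no provision found.
- Sensitivity analysis for withdrawals: none in SAP 4.4.1 or 4.4.2.

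**3. Illustration with five observed losses.** The documents give neither the number of withdrawals nor a number of expected losses, so these inputs are assumed: n = 46; losses at 0.5, 1.2, 2.5, 3.2 and 4.2 years; *w* subjects withdrawn and censored at 2.0 years; everyone else followed past 5 years.

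- Planned estimate: S(5) = 44/46 × (41 − w)/(44 − w)
- Proportion with graft had all been followed, if *k* of the withdrawn later lose it: 1 − (5 + k)/46

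| w | k | Planned KM | Complete follow-up | Gap (points, unrounded inputs) |
|---|---|---|---|---|
| 4 | 0 | 44/46 × 37/40 = 88.5% | 41/46 = 89.1% | −0.7 |
| 4 | 2 | 88.5% | 39/46 = 84.8% | 3.7 |
| 4 | 4 | 88.5% | 37/46 = 80.4% | 8.0 |
| 6 | 0 | 44/46 × 35/38 = 88.1% | 41/46 = 89.1% | −1.0 |
| 6 | 6 | 88.1% | 35/46 = 76.1% | 12.0 |

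The planned estimate does not respond to *k*. If all the withdrawn lose the graft, the gap is 8.0/4 = 2.0 or 12.0/6 = 2.0 points per subject.

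**4. A second set of assumptions.** Take the two graft losses reported in Table 1 (one each in studies 04 and 06) as early losses, then *w* withdrawals, then *L* later losses among those who stay. Compare censoring, 44/46 × (44 − w − L)/(44 − w), with counting every withdrawn subject as a loss, (44 − w − L)/46.

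| L | w | Censored | All withdrawn lost | Gap per withdrawn subject |
|---|---|---|---|---|
| 0 | 3 | 95.7% | 89.1% | 6.5/3 = 2.2 |
| 3 | 3 | 88.7% | 82.6% | 6.0/3 = 2.0 |
| 6 | 3 | 81.7% | 76.1% | 5.6/3 = 1.9 |
| 6 | 8 | 79.7% | 65.2% | 14.5/8 = 1.8 |

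Over the range tried, the bound is 1.8 to 2.2 points per withdrawn subject.

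**5. If censoring is not informative.** In step 3 with w = 4, those who stay lose 3 of 40 after year 2. At that rate the 4 withdrawn would have 4 × 3/40 = 0.3 losses, and 1 − 5.3/46 = 88.5%, equal to the planned estimate.

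**The case against.** The strongest reply is that the text supports less than it seems to at first sight.

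- A reader might infer that withdrawal under 4.3 ends all data collection. The section does not say so; it asks for notice to the monitor and a form. The defect is silence about later status, combined with a rule that censors at withdrawal.
- A reader might infer that footnote 1 is exhaustive and that sites will follow two rival rules. The footnote does not call its list complete, and nothing shows that sites differ. The mismatch stands; the divergence is not shown.
- A reader might infer that subjects returning to dialysis drop out of the graft curves. A known permanent return lasting at least 6 weeks is itself graft loss, and only withdrawal without graft loss is censored. For such a subject, at most a later death is missed.
- Investigators may have little reason to withdraw anyone, so no such withdrawals is plausible. That withdrawal tracks graft course is a possibility, not something the documents establish.
- The larger gaps need 4 or 6 withdrawals and loss of every graft among them. In step 3 with w = 4 the Greenwood standard error is about 4.9 points, giving roughly ±9.5, so one missed loss lies well inside the interval. Step 5 shows no bias when risks are equal. The illustration also does not separate subjects who withdraw consent to data, who would stay censored under any fix.
- Withdrawals are tabulated by time and reason, all 46 eligible subjects are accounted for, and the curve marks censoring. There is no hypothesis test.

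Most of this limits the size and leaves the gap in place. Tabulation lets a reader see withdrawals but does not recover their outcomes, and a confidence interval does not cover informative censoring.

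**Conclusion.** The point holds as a mismatch to reconcile and a gap worth closing. The investigator's right has no criteria and no counterpart in footnote 1. Graft and vital status after withdrawal are not provided for, and all three survival analyses censor at withdrawal without a sensitivity analysis. The resulting censoring is avoidable, and whether it is informative cannot be judged from the documents.

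The actual size is unknown. The figure of about 2 points of 5-year graft survival per unobserved loss is a bound that rests on n = 46 and assumed numbers and timing of losses and withdrawals. It is not a prediction, and with no investigator withdrawals this route has no effect. It matters because SAP 4.4.1 itself expects only a small proportion of graft losses among at most 46 subjects. The documents do not support a claim that the 5-year estimate is biased, nor that the investigator's right must be deleted.

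**What to change.** 1. **Protocol 4.3 and footnote 1.** Keep the investigator's right but limit it to stopping visits, samples and questionnaires, and make the footnote agree. Add to 4.3: *A subject who stops visits, or whose visits are stopped by the investigator, remains in the study. Graft status (with date) and vital status continue to be collected from the medical record or by telephone at each remaining time point up to 5 years, unless the subject withdraws consent to data collection.*
2. **End of Study Form.** Record separately whether the subject stopped visits or withdrew consent to data collection. Protocol 7.3 already treats consent for biological samples on its own.
3. **SAP 4.4.1 and 4.4.2.** Censor as withdrawals only subjects who withdrew consent to data collection and those truly lost to follow-up, in all three curves.

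**Cost.** A short amendment, one CRF field, possibly a sentence in the consent form, and brief chart review per stopped subject at each remaining time point. No new procedure is needed.

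**Timing.** SAP version 2.0 is dated April 2023, after the last visit planned for 2022. If visits are over, the sponsor can still retrieve status from records where consent allows and apply the change in censoring.
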